## 6.2 Randomisation

No randomization has been planned for this study as it is non-comparative.

# Statistical Analysis Plan

A Multi-center Outcomes Clinical Study of the PyroTITAN™ HRA Shoulder Implant in Humeral Head Resurfacing

Number: CP-HRA-002  
ST: ST1159  
Version: 1.0 05/Oct/2023  
Page: 7 of 19

## 6.3 Interim Analysis

A 5-year interim analysis will be carried out for this study.

# 7 STATISTICAL ANALYSIS

## 7.1 General

Smith + Nephew's Global Biostatistics group will conduct the statistical analysis for this study. Unless otherwise stated, all significance tests and hypothesis testing will be two-sided, performed at the 5% significance level. Resulting p-values will be quoted and 95% two-sided confidence intervals will be generated where appropriate. All p-values will be rounded to three decimal places, p-values less than 0.001 will be presented as '<0.001' in all tables.

Where data summaries are specified, categorical and ordinal variables will be summarized with frequencies and percentages. Continuous variables will be summarized with the following summary statistics: number of observations, mean, median, standard deviation, minimum and maximum values. All analyses will be performed in SAS 9.4 (or later).

## 7.2 Analysis Populations

The following subject populations will be used for the statistical analysis of this study.

- **Full analysis set population (FAS)**, following Intention to Treat principle including all subjects who are enrolled into the study.
- **Per-Protocol Population (PP)**, including all subjects in the full analysis set who have no significant protocol deviations and met the inclusion/exclusion criteria.
- **Per-Protocol Population 1(PP1)**, including all subjects in the full analysis set who have no significant protocol deviations and met the inclusion/exclusion criteria. This is the original cohort of subjects in the study who were enrolled prior to the additional proof testing and improvements in device inspection process. This population will be used for supporting analysis of the primary endpoint.
- **Per-Protocol Population 2(PP2)**, including all subjects in the full analysis set who have no significant protocol deviations and met the inclusion/exclusion criteria. This is the additional cohort of subjects who were enrolled after the additional proof testing and improvements in device inspection process. This population will be used for supporting analysis of the primary endpoint.

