## **6.2 Operative Management**

Each investigator will complete an Operative Details CRF based on source documentation that provides specific information from the Subject's surgery, such as surgical technique, catalog and lot numbers for implanted device. Any complications that occurred during the surgery are reported using the Operative Complications CRF.

The anesthesia procedure will follow the normal clinical practice at the investigation site. All sites are to use general, spinal or epidural anesthesia. Further, it is strongly encouraged that the anesthesia be standardized across all study Subjects within one institution.

In addition, each individual site will designate the surgical approach and any ancillary procedures on the Operative case report form. A surgical technique for the PyroTITAN™ HRA Shoulder prosthesis will be provided to each investigator participating in the study.

The Investigator should record all of the following information after the surgery:

- Subject Historical Profile
- Operative Detail
- Pre-op WOOS Score
- Pre-op ASES Score
- Pre-op Constant Score
- Pre-op Visual Analog Scale (Pain)
- Pre-Op X-rays, MRI and/or CT films

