## **11.3 Sample Size and Power Analysis**

The original sample size in this study was 150 enrolled subjects. Additional proof testing and improvements in the device inspection process were employed during the study, at which time it was determined that an additional cohort of subjects was necessary. We are now comparing a cohort of subjects enrolled after these changes to the original cohort of subjects.

With an expected attrition rate of 10% per annum, this will yield an evaluable sample size of 52 shoulders at ten years ( $150 * 0.9^{10} = 52.3$ , where 0.9 or 90% is the number expected to be retained from one year to the next). Based on past experience, we may obtain clinical follow-up on this number of shoulders, but we may obtain radiographic follow-up on as few as two-thirds of these shoulders (about 35 shoulders). This remaining number of evaluable shoulders with clinical and radiographic follow-up is adequate to establish a reliable ten-year survival estimate of survival for hemi arthroplasty (Dorey and Amstutz, 1986).

For the new cohort, the sample size is calculated based on the non-inferiority of the study device. The success rate for the study device is 96.1% from the original population and is used as reference rate. Therefore, for a conservative success rate of 96.1% of the study device is used in the study. The non-inferiority margin  $\delta$  of -0.033 is chosen in the study. 212 subjects are required to achieve  $100(1 - \beta) \% = 80\%$  power to detect non-inferiority at the Significance level of  $\alpha = 0.05$ . To account for 10% lost to follow-up, the

total number of additional subjects is 237. Therefore, the estimated enrollment for the study will be 387 subjects.

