## **18.0 Record of Device Inventory**

---

This is a post market study and all devices are CE marked. Therefore inventory control is not a regulatory requirement.

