## Statistical Analysis Plan

A Multi-center Outcomes Clinical Study of the PyroTITAN™ HRA Shoulder Implant in Humeral Head Resurfacing

Number: CP-HRA-002  
ST: ST1159  
Version: 1.0 05/Oct/2023  
Page: 15 of 19

$H_a$  = Alternative hypothesis that the success rate in the investigational group is non-inferior to the reference rate

$\delta$  = Non-inferiority margin pre-specified to be 3.3%.

The survival rate (the clinical success rate) will be calculated and the associated 95% exact confidence interval presented. If the upper 95% confidence limit is greater than the reference rate minus the non-inferiority margin ( $96.1 - 3.3 = 92.8\%$ ) then non-inferiority of the observed rate to the reference rate to within a 3.3% margin can be concluded.

Additionally, survival rate (the clinical success rate) and the associated 95% exact confidence interval at 2 and 5 years will be calculated and presented.

If data allows, time-to-event curves for device survival will be estimated using the Kaplan-Meier technique. For analysis of device survival, those lost to follow up or withdrawn from the study for reasons other than device revision or removal will be regarded as censored observations.

The primary analysis of this endpoint is to be carried out using the FAS population. The same analysis will be carried out on the PP population as supporting analyses.

As an additional analysis, the primary endpoint will be summarised for PP1 and PP2 populations in order to compare the cohort of subjects enrolled after the device changes to the original cohort of subjects.

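### The before/after-change cohorts (PP1, PP2) are assigned by time of enrolment, not by the implanted lot, and neither document ensures that the two agree

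*SAP*

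**What the plan says.** Protocol 11.3 explains why subjects were added: "Additional proof testing and improvements in the device inspection process were employed during the study". It then gives the aim of the enlarged study: "We are now comparing a cohort of subjects enrolled after these changes to the original cohort of subjects".

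SAP 7.2 turns this into two per-protocol subsets. PP1 is the original cohort, "who were enrolled prior to the additional proof testing and improvements in device inspection process". PP2 is described thus: "This is the additional cohort of subjects who were enrolled after the additional proof testing and improvements in device inspection process". SAP 7.4 lists a flag for each subset but gives no derivation, no calendar cut-off and no device criterion. SAP 7.9 uses the subsets for an additional summary of the primary endpoint, "in order to compare the cohort of subjects enrolled after the device changes to the original cohort of subjects".

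Two other places bear on the point. Protocol 6.2 has the investigator complete an operative form with details "such as surgical technique, catalog and lot numbers for implanted device". Protocol 18.0 notes that the devices are CE marked and concludes: "Therefore inventory control is not a regulatory requirement".

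**The concern.** The exposure of interest is whether the implant in the shoulder went through the extra proof testing and tighter inspection. That is a property of the implant. SAP 7.9 itself speaks of device changes. The flags, however, follow the time at which the subject entered the study, and the two can part company in either direction:

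- A subject enrolled after the change could receive an implant made and released before it, if such stock was still at the site.
- A subject enrolled before the change could be operated on afterwards with a post-change implant.

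Either way the cohorts become more alike than the devices are. An improvement from the new process would be understated, and a breakage in a pre-change implant could be counted against the improved one. Amendment 1 raised enrolment from 150 to 387, and the PP1/PP2 summary is the only analysis in the SAP that compares before with after.

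**Working it through.** **Does anything tie enrolment timing to device version?**

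- *Stock.* No passage says that pre-change implants were withdrawn, quarantined or re-tested. Protocol 18.0 shows only that the study requires no device inventory record.
- *Timing.* The pre-operative visit may fall up to 180 days before surgery (Protocol 2.0 and 6.3), and Protocol 16.0 treats a person as a study subject once consent is signed. Against that, Protocol 5.4 allocates a subject number only when eligibility is confirmed and surgery is to go ahead, and Protocol 6.5 treats people who consent but are excluded before surgery as screen failures. The gap is possible but narrower than 180 days suggests.
- *Cut-off.* The change is undated. PP1 is both the original cohort and those enrolled before the change; nothing shows that these are the same people.

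**The plan's own sample size, for reference.** Inputs from Protocol 11.3: rate 0.961, margin 0.033, alpha 0.05 (one-sided reproduces the figure), power 80%.

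- n = 0.961 × 0.039 × (1.645 + 0.842)² / 0.033² = 212.8, against 212 stated.
- 213 / 0.90 = 236.7, so 237; and 150 + 237 = 387, as stated.

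Reclassification changes none of this.

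**Effect of misassignment.** Let f be the share of PP2 with pre-change implants, g the share of PP1 with post-change implants, and p_old and p_new the success rates by device version. Assume that success depends on device version alone.

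- PP2 rate = (1 - f) × p_new + f × p_old
- PP1 rate = (1 - g) × p_old + g × p_new
- Observed difference = (1 - f - g) × (p_new - p_old)

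The documents give neither share. For illustration take p_old = 92.8% and p_new = 96.1%, a difference equal to the 3.3-point margin:

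| f | g | factor | observed difference (points) |
|---|---|---|---|
| 5% | 0 | 0.95 | 3.1 |
| 10% | 0 | 0.90 | 3.0 |
| 20% | 0 | 0.80 | 2.6 |
| 30% | 0 | 0.70 | 2.3 |
| 30% | 10% | 0.60 | 2.0 |

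**Scale against the noise.**

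- With 150 and 237 subjects, both at 96.1%, the standard error of the difference is √[0.961 × 0.039 × (1/150 + 1/237)] = 2.0 points, so the 95% half-width is about 4.0 points before any attrition.
- At 96.1% success, 212 subjects yield about 0.039 × 212 = 8.3 failures. One failure moves that cohort's rate by 1/212 = 0.47 points, or 14% of the margin.

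**The case against.** The case against is substantial, and much of it stands.

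- *Old stock in PP2 is inferred from silence.* Protocol 18.0 concerns study device accountability; it does not say that earlier stock stayed on the shelf. A withdrawal would be recorded in manufacturing files outside these documents. A reader might infer that PP2 does contain pre-change implants. No passage documents a single such subject; if stock was cleared before enrolment resumed, f is near 0.
- *The consent-to-surgery route is narrow.* Besides Protocol 5.4 and 6.5, Protocol 16.0 allows consent on the day of surgery. Protocol 11.3 also takes its 96.1% from the original population, so a good part of that cohort had presumably been operated on and followed when the new cohort was sized.
- *The number caught in a changeover cannot be derived.* A reader might multiply planned accrual by 180 days. The answer depends on the rate assumed: 150 over the initial twelve months is 12.5 a month, or about 74 subjects in 180 days (180/30.4 = 5.9 months); 237 over the remaining 36 of the 48 months is 6.6 a month, or about 39. If enrolment paused at the change it could be near zero. None of these is a usable bound.
- *A lot number does not by itself show proof-test status.* It must be linked to manufacturer records that neither document describes, and the change may not map cleanly to lots.
- *The analysis is supportive.* SAP 7.9 only summarises the endpoint by cohort, without a test or decision rule, and the illustrated shrinkage of 0.3 to 1.0 points (g = 0, f = 10% to 30%) is small beside a half-width of about 4 points.

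What remains is that the stated rule uses a proxy for the exposure, gives no cut-off, and leaves unused a better variable that is already collected.

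**Conclusion.** The point holds as a weakness in how a supporting analysis is defined. Enrolment timing stands in for device version, and the documents contain nothing that makes the two coincide. Any misassignment shrinks the PP1/PP2 difference by the factor (1 - f - g). The actual size is unknown because f and g are not given; the table is an illustration, and it assumes that success depends on device version alone.

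A reader might go further and conclude that the trial's main result is compromised. It is not. The primary test compares the full analysis set with a fixed 96.1%, and moving subjects between PP1 and PP2 leaves it unchanged. The point still deserves action because this summary alone answers the before/after question behind Amendment 1, and because with few failures expected, one event in the wrong cohort is visible.

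**What to change.** In SAP 7.2 and 7.4:

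1. Derive the PP1 and PP2 flags from the implanted lot number on the Operative Details form, linked to the manufacturer's proof-test and inspection records.
2. Use date of surgery, against a stated cut-off, only where the lot is missing or cannot be mapped. This fallback does not exclude old stock, so report how many subjects depend on it.
3. Cross-tabulate enrolment cohort against device version. If the two agree, that settles the matter.
4. Keep the enrolment-based split as a sensitivity analysis.

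Because the study is open, fix the rule before the cohorts are compared. The cost is SAP wording and one merge with manufacturer records. It needs no new subjects and no new data from sites. The downside is that a few subjects may not be classifiable by lot.

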# Statistical Analysis Plan

A Multi-center Outcomes Clinical Study of the PyroTITAN™ HRA Shoulder Implant in Humeral Head Resurfacing

Number: CP-HRA-002  
ST: ST1159  
Version: 1.0 05/Oct/2023  
Page: 8 of 19

- **Safety Population (SAF)**, including all subjects who have received any study treatment.

All safety analyses will utilise the SAF Population. All non-safety related endpoints will be analysed using both the FAS and PP analysis populations.

## 7.3 Handling of Missing, Incomplete and Repeat Data

Data will be analysed as observed in the study database.

## 7.4 Derived Data

### Analysis populations

- Flag for inclusion in the SAF population
- Flag for inclusion in the ITT population
- Flag for inclusion in the PP population
- Flag for inclusion in the PP1 population
- Flag for inclusion in the PP2 population

### Visit dates

- Pre-Operative visit within - 180 to -1 day window
- 3 month follow up within 1 - 120 day window
- 6 month follow up within 30 day window
- 12 month follow up within 60 day window
- 24 month follow up within 60 day window
- 36 month follow up within 90 day window
- 48 month follow up within 90 day window
- 60 month follow up within 90 day window
- 96 month follow up within 90 day window
- 120 month follow up within 90 day window

### Demographics

- $BMI \text{ [kg/m}^2\text{]} = \frac{weight \text{ [kg]}}{(height \text{ [cm]}/100)^2}$

### Surgery Details

- Surgical Time = End time of Operation – Start time of operation
- Time to discharge = Date of discharge – Date of Surgery

### Primary Endpoint

### CONFIDENTIAL AND PROPRIETARY

This document contains information that is confidential and proprietary to Smith & Nephew PLC and Smith & Nephew, Inc. and is intended for use only by Smith+Nephew and its manufacturer. It shall not be reproduced or copied in whole or in part, nor shall the contents be disclosed by any means without prior written permission from Smith+Nephew, nor shall anyone make any use of it that is contrary to the expressed or implied wishes of Smith+Nephew.

# Statistical Analysis Plan

A Multi-center Outcomes Clinical Study of the PyroTITAN™ HRA Shoulder Implant in Humeral Head Resurfacing

Number: CP-HRA-002  
ST: ST1159  
Version: 1.0 05/Oct/2023  
Page: 9 of 19

- Binary variable for clinical success (device survival), 1 if all the following are true and 0 if any is false:
  - A. Device remains implanted.
  - B. Absence of device-related complications requiring surgical replacement, removal, or augmentation of components.
  - C. Freedom from chronic dislocation.

A will be determined through absence of a removal/ revision

B will be determined through assessment of complications forms

C will be determined through assessment of Adverse Events

- Duration to intervention = Date of surgical intervention – Date of surgery

## VAS Pain and Satisfaction

Calculate the change from baseline VAS pain and VAS satisfaction scores to each visit (score at post-op visit minus score at baseline).

## ASES

The score is derived using the following equation:

$$\text{ASES score} = [(10 - \text{VAS pain score}) \times 5] + [(5/3) \times \text{Cumulative functional questions score (for operative side)}]$$

The pain score is copied from the VAS Form, which asks the subject to rate pain on a scale of 0mm no pain, to 100mm worst possible pain. This 100mm score will be converted to cm for the purposes of the ASES score calculation, by dividing by 10. This means the range of the VAS pain score will be 0 to 10.

There are 10 functional questions: put on a coat, sleep on the affected side, wash back/do up bra, managing toileting, comb hair, reach a high shelf, lift 10lbs above shoulder, throw a ball overhand, usual work, usual sport.

Assign the response to each functional question a score as follows:

- Unable to do = 0
- Very difficult to do = 1
- Somewhat difficult = 2
- Not difficult = 3

To calculate the cumulative functional questions score, sum the responses to the 10 questions (each response is worth a maximum of 3 points, maximum possible functional score of 30).

# Statistical Analysis Plan

A Multi-center Outcomes Clinical Study of the PyroTITAN™ HRA Shoulder Implant in Humeral Head Resurfacing

Number: CP-HRA-002  
ST: ST1159  
Version: 1.0 05/Oct/2023  
Page: 10 of 19

Calculate the ASES score for each visit, as well as the change from baseline score to each visit (score at post-op visit minus score at baseline).

## WOOS

There are 19 questions, each question is answered on a visual analogue scale ranging from 0 to 100. The questions are divided into four domains: Physical symptoms (max score 600), sports and work (max score 500), lifestyle (max score 500) and emotions (max score 300). The overall score ranges from 0 to 1900, with 1900 being the worst. For ease of interpretation, scores are converted to a percentage of the maximum score for each domain and overall [(score/max score)\*100].

Calculate the score for each domain and overall at each visit, as well as the change from baseline scores to each visit (score at post-op visit minus score at baseline).

## Constant-Murley

The Constant-Murley score is derived using the following equation:

$$\text{Constant-Murley score} = [\text{VAS pain score (0-15)} + \text{Cumulative ADL score (0-20)} + \text{Cumulative mobility score (0-40)} + \text{Maximum strength score (0-25)}]$$

The VAS Pain score refers to the question "Indicate the highest pain level you have experienced in your shoulder during ordinary activities within the last 24 hours" and ranges from 0 to 15.

Calculate cumulative ADL score as follows (maximum 20 points):

- Is your occupation or daily living limited by your shoulder?
  - No (4 points)
  - Moderate limitation (2 point)
  - Severe limitation (0 points)
- Is your leisure and recreational activities limited by your shoulder?
  - No (4 points)
  - Moderate limitation (2 point)
  - Severe limitation (0 points)
- Is your night sleep disturbed by your shoulder?
  - No (2 points)
  - Sometimes (1 point)
  - Yes (0 points)
- State to what level you can use your arm for painless, reasonable activities?
  - Waist (2 points)
  - Xiphoid (4 points)
  - Neck (6 points)
  - Head (8 points)
  - Above head (10 points)

# Statistical Analysis Plan

A Multi-center Outcomes Clinical Study of the PyroTITAN™ HRA Shoulder Implant in Humeral Head Resurfacing

Number: CP-HRA-002  
ST: ST1159  
Version: 1.0 05/Oct/2023  
Page: 11 of 19

Calculate cumulative mobility score as follows (maximum 40 points):

- Forward flexion
  - 0-30 (0 points)
  - 31-60 (2 points)
  - 61-90 (4 points)
  - 91-120 (6 points)
  - 121-150 (8 points)
  - $\geq 151$  (10 points)
- Abduction
  - 0-30 (0 points)
  - 31-60 (2 points)
  - 61-90 (4 points)
  - 91-120 (6 points)
  - 121-150 (8 points)
  - $\geq 151$  (10 points)
- External rotation – check all that apply
  - Hand behind head, elbow forward (2 points)
  - Hand behind head, elbow back (4 points)
  - Hand to top of head, elbow forward (6 points)
  - Hand to top of head, elbow back (8 points)
  - Full elevation (10 points)
- Internal rotation
  - Lateral thigh (0 points)
  - Buttock (2 points)
  - Lumbosacral junction (4 points)
  - Waist (6 points)
  - 12th vertebra (8 points)
  - Interscapular (10 points)

Calculate maximum strength score as follows (maximum 25 points):

If strength has been measured in kilograms, convert it to pounds by multiplying by 2.2.

Maximum strength score (in pounds) = max (1st attempt, 2nd attempt, 3rd attempt, 4th attempt, 5th attempt)

Calculate the CM score for each visit, as well as the change from baseline score to each visit (score at post-op visit minus score at baseline).

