### Strength

Strength is given a maximum of 25 points in the Constant Score. The significance and technique of strength measurement has been, and continues to be, the subject of much discussion.

The European Society for Shoulder and Elbow Surgery measures strength according to the following method:

- A spring balance is attached distal on the forearm.
- Strength is measured with the arm in 90 degrees of elevation in the plane of the scapula (30 degrees in front of the coronal plane) and elbow straight.
- Palm of the hand facing the floor (pronation).
- The patient is asked to maintain this resisted elevation for 5 seconds.
- It is repeated 5 times immediately after another.
- The average in pounds or kilograms (lb or kg) is noted.
- The measurement should be pain free. If pain is involved the patient gets 0 points.
- If patient is unable to achieve 90 degrees of elevation in the scapula plane the patient gets 0 points.

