## Constant Murley Score

The CM score consists of 4 domains: pain (15 points), activities of daily living (ADL) (20 points), movement (40 points) and power/strength (25 points). Strength score is calculated as the highest score of the 3 attempts.

Constant-Murley score questionnaires that are incomplete for the questions used for scoring at the baseline visit will not be included in the analyses.

The total score is calculated as the sum of each score from the 4 domains and ranges from 0 to 100 points, with a higher score indicating better shoulder function.

The CM score will be derived for each patient at each visit and summary statistics will be presented. Change from baseline score to each post-operative visit will also be presented. A paired sample t-test will be used to test changes in the scores from baseline to each post-operative visit. If the t-test assumptions are not met then a Wilcoxon Signed Rank test will be considered.

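### The SAP derives Constant strength points from the largest attempt in pounds without the protocol's two zero-point rules, and its formula has no step that enforces the stated 25-point maximum

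*SAP*

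**What the plan says.** Protocol 6.3, under Strength, gives the only strength method in the protocol. It sets the ceiling ("Strength is given a maximum of 25 points in the Constant Score") and describes a spring-balance test repeated five times, for which "The average in pounds or kilograms (lb or kg) is noted". It then gives two conditions under which the item scores nothing: "The measurement should be pain free. If pain is involved the patient gets 0 points" and "If patient is unable to achieve 90 degrees of elevation in the scapula plane the patient gets 0 points".

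SAP 7.4 (Derived Data, Constant-Murley) heads the item "Calculate maximum strength score as follows (maximum 25 points", adds "If strength has been measured in kilograms, convert it to pounds by multiplying by 2.2", and defines the score as the maximum over attempts one to five, in pounds. The formula carries no condition on pain or elevation.

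The equation for the total in SAP 7.4 gives strength a range of 0 to 25. SAP 7.10 repeats 25 points for strength and a total of 0 to 100. SAP 7.10 also says: "Constant-Murley score questionnaires that are incomplete for the questions used for scoring at the baseline visit will not be included in the analyses". SAP 7.3 has other data analysed as observed. SAP 7.14, which lists changes from the protocol's methods, names only the 5-year interim analysis.

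**The concern.** The protocol words its two rules as points, and the SAP is where points are computed. The SAP follows the protocol's set-up (five attempts, pounds or kilograms) but not the conditions that set the item to zero. A programmer working from SAP 7.4 would credit a painful or low-elevation pull with its full force.

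The study enrols end-stage shoulders (Protocol 5.3), so painful or restricted tests are plausibly most common before surgery. Unearned points there would raise the baseline mean and shrink the improvement. The Constant score is a named secondary endpoint, tested against baseline at each post-operative visit, and the protocol intends comparison with US and European data. That comparison needs the scoring the protocol describes.

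A second, smaller matter is that the formula line lets the item pass the ceiling the SAP itself states.

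**Working it through.** **Inputs.** The 25-point ceiling and both zero rules come from Protocol 6.3 (Strength). The factor 2.2 and the maximum-of-attempts formula come from SAP 7.4. The domain maxima and the 0 to 100 total come from SAP 7.4 and 7.10.

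**1. The plan's own total.**
- Activities of daily living: 4 + 4 + 2 + 10 = 20.
- Mobility: 4 items × 10 = 40.
- Total: 15 (pain) + 20 + 40 + 25 (strength) = 100.

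This reproduces the stated 100. Daily living and mobility reach their maxima by construction. Strength is the measured force itself, so it stays within 25 only if something holds it there.

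**2. Zero rules.** Take a largest attempt of 8 kg, recorded with pain.
- SAP 7.4: 8 × 2.2 = 17.6 points.
- Protocol 6.3: 0 points.
- Excess: 17.6 points on a 100-point scale for that subject and visit.

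**3. Effect on a visit mean.** The documents do not say how often a zero rule applies or what force is recorded when it does. As an assumption, let a share *s* of subjects meet a zero rule with a force of *f* pounds recorded. The mean is then too high by *s* × *f*.

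| Share *s* | *f* = 3 lb | *f* = 5 lb | *f* = 10 lb |
|---|---|---|---|
| 10% | 0.3 | 0.5 | 1.0 |
| 30% | 0.9 | 1.5 | 3.0 |
| 50% | 1.5 | 2.5 | 5.0 |

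The shift is zero if assessors already enter 0 in these cases.

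**4. Ceiling.** The formula reaches 25 points at 25 / 2.2 = 11.4 kg. Read literally above that, with the other domains at their maxima (15 + 20 + 40 = 75):
- 12 kg: 12 × 2.2 = 26.4; total up to 75 + 26.4 = 101.4.
- 15 kg: 15 × 2.2 = 33.0; total up to 108.0.
- 20 kg: 20 × 2.2 = 44.0; total up to 119.0.

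**5. Direction.** Unearned points at baseline make the change from baseline too small. Untruncated points at follow-up make it too large. Unearned points at follow-up also make it too large. The documents do not give the balance.

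**6. Blanks.** If a site left the attempts blank because the test could not be done, a protocol-defined zero would become missing. At baseline, SAP 7.10 would then exclude the questionnaire. After surgery, SAP 7.3 gives no rule for scoring it.

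**The case against.** The strongest reply is that the zero rules belong to data capture. Protocol 6.3 lists them among the steps of the test, and the Constant form is completed from source documentation. If the assessor enters 0 as the protocol directs, the maximum of the attempts is 0 and the SAP formula gives the right answer. SAP section 2 names the protocol and the case report form as related documents, so it could be said not to need to repeat them. This is possible, but the documents do not show it: the form is not included, and the SAP computes points from the attempts without saying that zeros have already been applied.

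Several stronger readings are tempting and are not supported:

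- **That the SAP has no ceiling.** It states 25 points in the heading of the item, in the equation for the total and in 7.10. Only the truncation step is absent, and a careful programmer might supply it.
- **That the missing truncation favours weak shoulders.** It matters only above 11.4 kg, so it concerns strong ones.
- **That scoring in pounds is itself wrong.** The protocol allows pounds or kilograms and gives no other conversion from force to points.
- **That the weakest shoulders will be dropped as incomplete.** This needs a blank field, and the exclusion in 7.10 applies to the baseline form only. Whether sites enter a force, 0 or a blank is unknown, so no count of lost subjects can be given.
- **That the errors must add up.** The baseline and ceiling effects on the change score have opposite signs and may partly offset.

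It is also fair to say that this is one of several secondary endpoints in an uncontrolled study that the protocol calls exploratory.

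**Conclusion.** The point stands in a limited form. The SAP's strength derivation omits both protocol zero-point rules and does not declare the departure, so any force recorded with pain or below 90 degrees earns points that the protocol sets to 0 (17.6 for an 8 kg pull). The formula line also lacks the step that would enforce the SAP's own ranges of 0 to 25 and 0 to 100.

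Under the assumed shares and forces, a visit mean would be 0.3 to 5.0 points too high from the zero rules. That range is illustrative and rests on a force having been recorded in those cases. The net size and direction for change from baseline cannot be determined from the documents. The primary endpoint is not touched. It is worth correcting because the text change is short and prevents a wrong secondary-endpoint score.

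**What to change.** Reconcile SAP 7.4 with Protocol 6.3 and state, for every visit:

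- strength points = 0 where the record shows that the test was painful or that 90 degrees was not reached, including attempts left blank for that recorded reason;
- otherwise strength points = min(25, strength in pounds by the reconciled attempt rule);
- strength is missing only when no such reason is recorded.

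The attempt rule is a separate matter to settle at the same time: the protocol notes the average of five repeats, SAP 7.4 takes the largest of five, and SAP 7.10 the highest of three.

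The cost is a few lines of SAP text and programming, with one check first: confirm that the case report form or source captures pain during the test and elevation. The fields visible in the SAP are flexion and abduction bands and the highest pain in ordinary activities over 24 hours, and these may not be enough. Where the information was not captured, site queries are needed; failing that, declare the departure in SAP 7.14.
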